#### **1** Background Information and Scientific Rationale

#### 1.1 Scientific Background and Preliminary Data

[figure not shown]
Glucocorticoids are among the most frequently prescribed immunosuppressive and antiinflammatory medications worldwide (1, 2). Long-term use, however, is complicated by serious non-immunologic side effects. A large gap of knowledge about the differences between the actions of this class of drugs on immune and non-immune cells has prevented the development of more targeted therapies or the use of drug combinations that would preserve the desired immunological effects while avoiding unwanted systemic activities. Glucocorticoids are ligands for a nuclear receptor and their mechanism of action involves broad effects on gene expression via binding to the well-recognized mammalian glucocorticoid response element (GRE). Recent

[figure not shown]
**Figure 1.** (A) Genome-wide view of the transcriptional response 2 hours after in vitro stimulation with 1  $\mu$ M dexamethasone in lymphoblasts (outer circle) and fibroblasts (inner circle). Each dot corresponds to a gene. Genes that are differentially expressed (dexamethasone versus vehicle) will appear higher in the plot. The black line represents a differential expression q-value of 0.01 (-log10 q-value = 2). Genes marked in red are differentially expressed in lymphoblasts but not in fibroblasts, as seen in the close-up of chromosome 4 (B).

discoveries, including that of a negative GRE (3, 4) and of a glucocorticoid-responsive long noncoding RNAs (5) suggest that other important aspects of drug action at the genome level remain incompletely characterized. Ongoing in vitro experiments with human cells in our laboratory suggest that there are indeed fundamental differences in the genomic response of immune and non-immune cells to glucocorticoids (Figure 1).

[figure not shown]
We have identified genes that are known to be involved in immune function and are differentially expressed in immune but not in non-immune cells after in vitro exposure to glucocorticoids. Within this group, we have observed genes that increase and genes that decrease in expression after glucocorticoid stimulus (Figure 2).

This includes genes that had been previously observed to respond to glucocorticoids (e.g., decreased expression of the cytokines IL1B and TNF), as well as genes that were previously not known to be affected by glucocorticoids (e.g., increased expression of KLF2, a transcription factor involved in T cell quiescence, regulation of T cell migration(6), negative regulation of B cell clonal expansion (7), and regulation of acute and chronic inflammation (8)). In addition, the genome-wide view of the transcriptional response provided by RNA sequencing has given us a more complete picture of the effects of glucocorticoids on hematopoietic and non-hematopoietic cell types than was previously available. Among genes that are differentially expressed in hematopoietic but not in non-hematopoietic cells after a glucocorticoid stimulus, we have observed a strong representation of TNF signaling molecules (decreased expression of TNFSF11, TNFSF14, TNF, LTA, and LTB), TLR signaling molecules (decreased expression of TLR1, TLR6, CCL3, CD80, and CCL4), and genes known to be involved in leukocyte migration and margination (CXCR4, CXCR5, KLF2).

Importantly, a number of genes known to be involved in immune function and differentially expressed in lypmhoblastoid cells are not expressed at all in fibroblasts (Figure 3), providing support for the hypothesis that there are potential targets for mimicking the immunologic effects of glucocorticoids without direct adverse consequences on non-immune cells.

**Figure 3.** Many of the immune genes that are differentially expressed in lymphoblasts at 2 and 6 hours are not expressed at all in fibroblasts. Expression levels are displayed in fragments per kilobase of transcript per million mapped reads (FPKM) in an RNA sequencing experiment 2 hours after stimulation with 1  $\mu$ M dexamethasone. The 3 columns on the left are technical triplicates of a fibroblast culture, and the 3 columns on the right are technical triplicates of a lymphoblast culture.

Finally, our in vitro data suggests that there is a significant and differential response of the noncoding genome to the glucocorticoid stimulus: Approximately 16% of the transcripts that are differentially expressed in lymphoblasts but not in fibroblasts after a glucocorticoid stimulus correspond to long-non-coding RNAs (Table 1).

	2 hours	6 hours
Total transcripts DE in lymphoblasts but not in fibroblasts	586	2047
IncRNA transcripts DE in lymphoblasts but not in fibroblasts	96	315
Proportion of DE transcripts that are IncRNA	16.4%	15.4%

#### FDR for differential expression: 0.01

**Table 1.** Approximately 16% of the transcripts that are differentially expressed in immune but not in non-immune cells after a glucocorticoid stimulus correspond to long non-coding RNAs. FDR=False Discovery Rate

At the completion of this study, we expect to generate a list of human genes and non-coding RNAs that are differentially expressed and regulated in response to glucocorticoids between immune and non-immune cells in vivo. These data will be used to identify transcripts, their corresponding proteins, and the molecular pathways that are best candidates for targeted intervention. Potential targets could then be validated with siRNA libraries, with the long-term goal of developing small-molecule (9, 10) or nanoparticle-facilitated-RNAi (11, 12) interventions that reproduce the therapeutic action of glucocorticoids in immune cells while avoiding the harmful side effects of this class of drugs on other tissues.

#### 1.2 Rationale for Performing the Study in Healthy Subjects

While the long-term goal of this line of research is to allow the development of targeted therapeutic interventions for people with inflammatory and autoimmune disorders, the immediate obstacle to accomplishing that goal is a lack of understanding of the human genomic response to glucocorticoids in immune and non-immune cells. The immediate goal of this study is to understand this response. For that purpose, one could start with either patients or healthy volunteers. However, patients who require glucocorticoids, even with a common clinical indication, show great variability in terms of disease state, co-morbidities, and the use of other immunosuppressive and anti-inflammatory drugs. For an initial study, these strong confounders would likely obscure the identification of the specific effects of glucocorticoids, and would likely require a large number of subjects to reach an answer that could potentially be obtained by studying a smaller number of less clinically variable subjects, such as healthy volunteers.

likely be higher in patients with significant co-morbidities and additional immunosuppressive drugs than in a well-selected cohort of healthy volunteers. Therefore, the safest and most scientifically rational approach to the question of how the human genome responds to glucocorticoids is to perform an initial study in a cohort of healthy volunteers, and to use the results obtained in this cohort as the basis for designing and interpreting future studies in patients with inflammatory and autoimmune disorders.

#### 1.3 Choice of a Glucocorticoid and Routes of Administration

Chemical modifications to the 21-carbon corticosteroid backbone (e.g. introduction of a carbon 1-2 double bond, methylation at carbon 6, fluorination at carbon 9), have led to the diverse set of glucocorticoids that is currently available for clinical use. These modifications have mostly altered the pharmacokinetic properties of the drugs, and the relative proportion of mineralocorticoid and glucocorticoid activity, but they do not appear to have significantly altered the mechanism of action or the side effect profile of glucocorticoids. Therefore, the choice of a specific glucocorticoid for our study was based on the frequency of its use in clinical practice, the availability of reports of safe use in studies of healthy human volunteers, and the availability of an intravenous formulation (to reduce potential inter-individual variation in rates of absorption). Methylprednisolone is widely used in clinical practice, with indications in the management of diverse conditions including dermatomyositis (13), lupus nephritis (14), acute asthma exacerbations (15), and relapses of multiple sclerosis (16). Intravenous methylprednisolone has been used in multiple studies of healthy volunteers since the early 1970s (17-19), without reports of serious adverse events (SAEs) in those studies. Sodium succinate and phosphate esters are available for intravenous use. Therefore, we have identified methylprednisolone sodium succinate as the glucocorticoid of choice for our study. Because our study involves a comparison of the effect of glucocorticoids in immune and non-immune cells, in addition to blood we will serially sample a non-hematopoietic tissue. Skin is composed mostly of non-hematopoietic cells and is easily accessible, so we have selected the skin as a nonhematopoietic tissue for sampling. It is unclear from existing literature whether the concentrations of methylprednisolone in skin after intravenous administration are sufficient to induce gene expression changes after short-term administration. However, high concentrations of methylprednisolone in the skin can be achieved with topical administration. Although topical methylprednisolone is widely used in clinical practice around the world, an IND application will be required for topical methylprednisolone use in our study given that topical methylprednisolone is not currently marketed in the United States.

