# 3 Study Design

Healthy volunteers will present to the NIH CC for a brief screening visit. A baseline whole-blood sample will be obtained on the screening day from volunteers who are eligible for the study and choose to enroll. Enrolled volunteers will return for a day-long study visit ("infusion visit"): following a pre-infusion whole-blood sample, volunteers will receive a single intravenous dose of 250 milligrams (mg) of methylprednisolone sodium succinate infused over 30 minutes. Whole-blood samples will then be obtained serially, in one of two regimens: 1 and 2 hours or 2 and 4 hours after the start of drug administration. A 3-mm skin punch biopsy sample may be obtained prior to IV methylprednisolone administration. If so, a single application of topical methylprednisolone 0.1% will be applied to a small area (2 x 2 cm) of the skin contralateral to the baseline biopsy site post IV methylprednisolone administration, and a second skin punch biopsy will be performed 4 hours after the start of drug administration in the area of skin where topical methylprednisolone was applied. Samples will be processed as follows:

Visit	Volunteer sample	Initial processing	Downstream use
Screening	·	10 mL: Complete blood count, acute care panel, prothrombin time (PT) & partial thromboplastin time (PTT), interferon gamma release assay (IGRA), and serum pregnancy test	NA
		10 mL: HIV and hepatitis A, B and C testing	NA
	Baseline whole- blood sample	5 mL: DNA purification	Genome-wide genotyping and/or DNA sequencing
visit	(103 mL)	8 mL: Plasma purification	Plasma banking
		60 mL: Isolation of hematopoietic cell sub-types (e.g. neutrophils, B cells, CD4+ T cells, CD8+ T cells, monocytes, NK cells) a	RNA-level, DNA-level, protein-level, and/or functional assays
		10 mL: PBMC isolation	PBMC banking
	Pre-infusion and 4-hour skin	Fibroblast isolation and establishment of a fibroblast cell line	In vitro exposure of fibroblasts to glucocorticoids iPS generation for in vitro
	biopsies (up to 3 mm x 2)		study of other non- hematopoietic cell types
		RNA isolation	RNA sequencing Small-RNA sequencing
		60 mL: Isolation of hematopoietic cell sub-types (e.g. neutrophils, B cells, CD4+ T cells, CD8+ T cells, monocytes, NK cells)	RNA-level, DNA-level, protein-level, and/or functional assays
	Pre-infusion whole-blood	10 mL: PBMC isolation	PBMC banking
Infusion visit Serial post- infusion whole- blood samples	sample	8 mL: Plasma purification	Plasma banking

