	5 mL: Complete blood count, acute care panel and serum pregnancy test	NA	
		5 mL: Serum	Concentration of methylprednisolone
	infusion whole-	60 mL: Isolation of hematopoietic cell sub-types (e.g. neutrophils, B cells, CD4+ T cells, CD8+ T cells, monocytes, NK cells)	RNA-level, DNA-level, protein-level, and/or functional assays
		10 mL: PBMC isolation	PBMC banking
		8 mL: Plasma purification	Plasma banking
		5 mL: Complete blood count and acute care panel	NA
		5 mL: Serum	Concentration of methylprednisolone

**Table 2.** Processing and use of samples from healthy volunteers

aThe purpose of this initial sample will be to assess the level of variation in the baseline.

Abbreviations: iPS induced pluripotent stem (cells), NA not applicable, NK natural killer, PBMC: Peripheral blood mononuclear cell, TBNK: Flow cytometry panel for T lymphocytes, B lymphocytes, and NK cells

Volunteers will be discharged after collection of the 2-hour or 4-hour blood and biopsy samples (depending on the regimen of blood collection), measurement of vital signs, and documentation of any AEs. Follow-up phone calls 1 day and 5 days after discharge will document any adverse effects related to the drug or skin biopsy. If any AEs that may require treatment are documented on the follow-up phone calls, volunteers will be asked to come to the NIH CC's outpatient clinic for evaluation by the Principal Investigator.

We propose an adaptive study design, in which we will recruit an initial cohort of 20 subjects. After processing the samples from these subjects, we will perform differential expression analysis to determine if recruitment of additional subjects (up to a maximum of 50) would impact the biological interpretation of the data. If additional data would be unlikely to change the study outcome, then no further recruitment will be pursued.

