#### 5.1.3 Dosage and Administration

Study volunteers will receive 250 milligrams administered intravenously over 30 minutes.

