#### 5.2.2 Formulation

1g Advantan emulsion 0.1% (Bayer) contains methylprednisolone aceponate (21-acetoxy-11beta-hydroxy-6alpha-methyl-17-propionyloxy-1,4-pregnadiene-3,20-dione) 1 mg, as the active ingredient. It is an oil-in-water emulsion containing medium chain triglycerides, caprylic-capricstearic triglyceride, polyoxyethylene alcohol 2-stearylether, polyoxyethylene alcohol-21stearylether, benzyl alcohol, disodium edetate, glycerol, and purified water.

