#### 5.2.3 Dosage and Administration

Advantan emulsion 0.1% will be applied thinly to the skin in a 2 x 2 cm area. This is a one-time application.

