lymphoid). They will also be used for pathway enrichment analysis, to determine the molecular pathways and biological functions that are most responsive to the glucocorticoid stimulus in each cell type. The genes and pathways that are found to be modified by the glucocorticoid stimulus in immune cells but not in non-immune cells (skin cells from this in vivo study and the primary human cells we have studied in vitro), will be selected as the top candidates for targeted therapeutic intervention, which we expect will form the basis of future studies.

Sequencing library preparation and sequencing batches will be carefully designed such that samples from the same subject and cell type are run in the same batch and samples from different subjects are evenly distributed across batches. This will keep batch effects to a minimum in the identification of differentially expressed genes. For analyses across different subjects, such as comparisons among different cell types, linear regression will be adopted with batch as regression variable to adjust for batch difference. While prior experience suggests that library preparation is the greatest source of batch-to-batch variation in RNA-seq experiments, if the source of batch effects is unclear or cannot be adequately modeled, the R package SVA will be used.

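### The candidate rule counts no change in skin as evidence that a gene is immune-only, but no prespecified criterion shows that the biopsied skin had a transcriptionally active exposure

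*Combined protocol and SAP*

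**What the plan says.** **Immune cells.** Section 5.1.3: "Study volunteers will receive 250 milligrams administered intravenously over 30 minutes". The drug is the sodium succinate ester. Table 2 (section 3) assigns 5 mL of serum from the pre-infusion and each post-infusion sample to "Concentration of methylprednisolone". The Précis says serum and the Protocol Summary says plasma; either way the level is a blood level.

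**Skin.** Section 1.3 first states a doubt about the intravenous route: "It is unclear from existing literature whether the concentrations of methylprednisolone in skin after intravenous administration are sufficient to induce gene expression changes". The next sentence gives the protocol's answer: "high concentrations of methylprednisolone in the skin can be achieved with topical administration". No figure or reference supports it. Section 3 then specifies, relative to where the first biopsy was taken, that "a single application of topical methylprednisolone 0.1% will be applied to a small area (2 x 2 cm) of the skin contralateral". Section 5.2.3 adds: "Advantan emulsion 0.1% will be applied thinly to the skin in a 2 x 2 cm area. This is a one-time application". By section 5.2.2, the emulsion "contains methylprednisolone aceponate", a different ester from the infused drug. The second biopsy is taken from the treated site 4 hours after the start of the infusion (sections 3, 6.2 and 7). It is optional, and the number of volunteers biopsied is not stated.

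**Use of the skin result.** Section 14 makes a list of differentially expressed transcripts in skin part of the primary endpoint, at FDR below 5%. Genes and pathways that change in immune but not in non-immune cells "will be selected as the top candidates for targeted therapeutic intervention". Non-immune here means the skin from this study and the primary human cells already studied in vitro.

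**The concern.** The skin comparison is informative about cell type only if the skin cells saw enough drug to respond. The protocol doubts one route, asserts the adequacy of the other, and measures neither at the biopsy site. Section 14 contains no skin drug level, positive-control transcripts, minimum response or vehicle comparison that must be satisfied before a gene is called unmodified in skin.

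At stake is the meaning of the in vivo immune-versus-skin list. A gene that responds to glucocorticoids in both tissues would appear immune-only if its skin sample were under-exposed. This is separate from the question of how non-response is tested. A formal test of the difference in response, applied to under-exposed skin, would correctly find a difference, but one due to exposure.

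**Working it through.** **1. What is and is not verified**

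| | Immune cells | Biopsied skin |
|---|---|---|
| Infusion, 250 mg | yes | yes; adequacy for skin called unclear (1.3) |
| Topical aceponate | no | yes; adequacy asserted (1.3) |
| Drug level measured | yes, in blood | no |
| RNA sequencing before and after | yes | yes, where biopsied (Table 2) |
| Preset criterion for an active exposure | none | none |
| Role in the candidate rule | must change | must not change |

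The last row creates the asymmetry. Under-exposure of immune cells would lose candidates; under-exposure of skin would add false ones.

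**2. The plan's own figure**

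The initial cohort of 20 (maximum 50) is argued from a pilot study of hydrocortisone. The documents give no SD, target power or per-gene significance level, so it cannot be reproduced as a power calculation. What follows is illustration only.

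**3. Failure of topical delivery in some volunteers**

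Assumed inputs, none from the documents: true skin log2 change 1.0 when exposure is adequate; SD of the paired change 0.7; two-sided p < 0.001 as a stand-in for 5% FDR; a share *u* of volunteers with topical failure; a fraction *r* of the full response delivered by the infusion alone.

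- Mean change = 1 − *u*(1 − *r*)
- SD = √(0.7² + *u*(1 − *u*)(1 − *r*)²)
- Power of the paired t-test = P(|T| > critical value), with T noncentral t on *n* − 1 degrees of freedom and noncentrality √*n* × mean/SD. The mixture of volunteers is treated as normal.

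For *n* = 20 the critical value is 3.883.

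| *u* | *r* | Mean | SD | Noncentrality | Detection in skin |
|---|---|---|---|---|---|
| 0 | – | 1.000 | 0.700 | 6.39 | 98% |
| 0.25 | 0 | 0.750 | 0.823 | 4.08 | 58% |
| 0.50 | 0 | 0.500 | 0.860 | 2.60 | 15% |
| 0.25 | 0.5 | 0.875 | 0.733 | 5.34 | 90% |
| 0.50 | 0.5 | 0.750 | 0.743 | 4.51 | 72% |

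With 10 skin pairs and *r* = 0, detection is 47%, 12% and 3% for *u* = 0, 0.25 and 0.50.

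**4. Uniform under-exposure, and whether more volunteers help**

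Take a gene with the same true response in both tissues, log2 change 0.5 (the pilot study's cut-off, section 14), assumed SD 0.5 and p < 0.001. Skin shows a fraction *f* of the response. With independent errors, the share of such genes that look immune-only once detected in immune cells is 1 minus power in skin.

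| *f* | 20 pairs | 50 pairs |
|---|---|---|
| 1 | 29% | about 0% |
| 0.5 | 91% | 48% |
| 0 | 99.9% | 99.9% |

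At p < 0.005 the 20-pair column is 12%, 79% and 99.5%. Over SD 0.4 to 0.7 and both p-values it runs from about 2% to 70% at full response and from 62% to 97% at half. A larger sample reduces the error when exposure is partial and does nothing when it is absent. The 29% at full response is ordinary lack of power and is not part of this point.

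**5. Passages on skin exposure that disagree**

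Section 3 places the topical application after the infusion, while section 6.2 lists it before. Since the biopsy is timed from the start of the infusion, skin contact time is not fixed. The emulsion strength is 0.1% in sections 3, 5.2.2 and 5.2.3 and 1% in section 11.2.

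**The case against.** The strongest reply has four parts.

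- **The doubt was answered.** It concerns the intravenous route, and topical dosing was added because of it. This stands: the issue was not overlooked. What remains is that the answer is asserted and not checked in these volunteers.
- **The skin is not simply given another route.** A reader might infer that skin receives only the topical drug, so that topical failure means unexposed skin. Sections 3 and 6.2 do not support that, because every biopsied volunteer also receives the infusion. Section 1.3 calls delivery by that route unclear, not absent. This is why the working shows *r* = 0.5 beside *r* = 0, and the loss is then much smaller. Nor do the documents show any harm from the different ester as such.
- **A response would be visible.** A reader might infer that nothing in the trial could reveal a failure. Paired skin RNA sequencing is planned and a skin list is part of the primary endpoint, so a general failure would appear as a near-empty list. This stands. A weak list, or failure in only some volunteers, would still have no agreed interpretation.
- **There is a second filter.** The in vitro non-immune cells had controlled exposure, and biopsy fibroblasts will also be exposed in vitro. Shared genes seen there can be removed whatever happened in skin, so the percentages above do not carry over to the final candidate list. The documents do not allow the residual to be computed. The filter does not protect the in vivo immune-versus-skin contrast itself.

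**Conclusion.** The point holds for the in vivo immune-versus-skin contrast and, to a lesser and unknown degree, for the candidate list. The plan uses non-response in skin as evidence without a prespecified criterion that the skin was actively exposed.

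Under the assumed inputs with 20 skin pairs, topical failure in a quarter to a half of volunteers takes detection in skin from 98% to between 58% and 15% if the infusion contributes nothing, or between 90% and 72% if it contributes half the response. The effect size, SD, p-value, failure share, infusion contribution and number of skin pairs are all assumptions. The documents do not establish that skin is in fact under-exposed, and this point does not claim it. The later work is exploratory and functional validation is planned, which limits the harm. The gap is still worth closing, because closing it needs no new sample.

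**What to change.** Add the following to section 14, before the skin/immune contrast is examined.

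1. **Control set.** Fix a list of transcripts that respond in both fibroblasts and lymphoblasts in the sponsor's in vitro data, with the expected direction of each. The protocol reports counts only for transcripts that respond in lymphoblasts but not fibroblasts, so the sponsor must first confirm that the shared set is large enough.
2. **Overall check.** Test the set as a whole in the paired pre-infusion and 4-hour skin samples, with the test and pass criterion stated in advance. Use in vivo skin as evidence of non-response only if the set moves in the expected direction overall. Otherwise base immune-only calls on the in vitro non-immune cells, and say so in the report.
3. **Volunteer-level scores.** Report each volunteer's control-set score and use the scores in a sensitivity analysis, not as a hard exclusion. Each volunteer has a single pair, and discarding exposed pairs is costly: with the inputs of step 3 of the working, going from 20 to 15 fully exposed pairs lowers detection from 98% to 88%.
4. **Reconcile the text.** Make sections 3 and 6.2 agree on when the topical agent is applied relative to the infusion. Make sections 3, 5.2.2, 5.2.3 and 11.2 agree on emulsion strength.

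The cost is analysis wording and a protocol correction, with no new samples or assays. Control transcripts cannot be candidates, although they already respond in an in vitro non-immune cell and the existing rule should exclude them. A failed check may reflect tissue composition or timing, since the in vitro data are from cultured cells at 2 and 6 hours. It therefore limits what may be claimed from skin and does not prove lack of exposure.
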